4.9 Definitions

Aortic aneurysm enlargement: $\geq 5\text{mm}$ as compared to any previous CT measure using orthogonal (i.e., perpendicular to the centerline) measurements

Aortoiliac aneurysm: aneurysm of the abdominal aorta and including one or both of the iliac arteries

Aneurysm-related mortality:

Death occurring within 30 days or during hospitalization following the index procedure, unless there is evidence of accidental or self-inflicted death;

Death occurring within 30 days or during hospitalization following conversion to open repair or a secondary intervention for migration, Type I and III endoleaks, device integrity failure (e.g., fracture), or patency-related events (i.e., device stenosis or occlusion and embolic events), unless there is evidence of accidental or self-inflicted death;

Death occurring within 30 days or during hospitalization for a complication of the aneurysm or a complication associated with the device, such as:

- aortic rupture
- fistula formation (e.g., aorto-enteric)
- embolization
- malperfusion of organ(s) or limb(s)

Arterial fistula formation: formation of an abnormal connection or passageway between an artery and adjacent structures

Conversion to Open, Early: any open repair within 30 days of the index procedure involving the vasculature in the abdomen and/or pelvis.

Conversion to Open, Late: any open surgical repair involving stentgraft removal after 30 days post index procedure

Chronic Obstructive Pulmonary Disease (COPD): forced expiratory volume (FEV1) < 1.0 liter or receiving home oxygen

Crawford Type IV TAAA: aneurysmal dilatation originating within 5cm of the celiac artery

Disabling stroke: Modified Rankin Score MRS >2

Distal landing zone: aortic fixation site furthest from the heart

Embolization: dislodging of an upstream particle that travels downstream causing blockage of free flow further downstream. Embolization could result in malperfusion

Embolus: blood clot that forms at one location (presumably from the aneurysmal sac, aortic neck, or adjacent vessels) and is dislodged to another location resulting in ischemic changes

Emergent: an aneurysm requiring immediate treatment

Endoleak:

Type I: leak occurring at the proximal or distal fixation site, including leakage around fenestrations

Type Ia: leak occurring at the proximal fixation zone of the stent-graft

Type Ib: leak occurring at the distal fixation zone of the stent graft

Type Ic: leak occurring at the distal fixation zone of the covered stents in the visceral vessels incorporated by the fenestrations

Type II: leak caused by retrograde flow from patent lumbar or inferior mesenteric arteries

Type IIIa: leak caused by a defect in the graft fabric

Type IIIb: leak caused by inadequate seal between modular graft components

Type IV: leak caused by graft fabric porosity, often resulting in a generalized blush of contrast within the aneurysm sac .

Endoleak, Early: any endoleak observed within 30 days after device deployment

Endoleak, Late: any endoleak observed later than 30 days after deployment that was not documented during the first 30 days after deployment

Estimated Glomerular Filtration Rate (eGFR): estimated GFR (mL/min/1.73 m²) = 175 x (Serum creatinine)-1.154 x (Age)-0.203x (0.743 if female) x (1.210 if African-American)

Limb occlusion: the presence of thrombus within any graft limb that creates occlusion

Major adverse events: all-cause mortality, bowel ischemia (requiring medical or surgical management), myocardial infarction, paraplegia, renal failure, respiratory failure, and stroke

- **All-Cause Mortality:** any death occurring within the first 30 days post procedure
- **Bowel Ischemia:** Bowel ischemia due to limb or arterial occlusion, graft placement, or embolization.
- **Myocardial infarction:** raised levels of cardiac biomarkers or ECG changes
- **Paraplegia:** spinal cord ischemic event resulting in complete loss of motor function with or without loss of sensation in the lower extremities

- **Renal Failure:** acute or progressive renal insufficiency leading to the need for dialysis or hemofiltration
- **Respiratory failure:** Prolonged intubation (>48 hours after spinal drain removal or >72 hours total) and/or reintubation. This definition does not put the patient at any increased risk. The high risk patient population being treated in this study is prone to pre-existing comorbidities, including COPD and decreased respiratory function, and may require extended ventilator support while in the supine position for spinal drainage.
- **Stroke:** neurological deficit that lasts > 24 hours

Malperfusion of organ(s) or limb(s): loss of flow through a particular vascular bed has been partially or completely compromised leaving the said organ or limb ischemic

Migration, clinically significant: antegrade or retrograde migration that requires surgical or endovascular intervention

Paraparesis: spinal cord ischemic event resulting in partial neurologic deficit in the lower extremities

Parietal arteries (branches): inferior phrenic, lumbars and middle sacral arteries

Patency: the state of a vessel that has unimpeded flow into and out of the vessel

Proximal landing zone: the aortic fixation site closest to the heart

Proximal fixation length: the aortic fixation site measured from the proximal edge of the graft to the start of the aneurysm

Renal insufficiency: rise in serum creatinine of more than 50% above pre-procedure level which results in a serum creatinine >2.0 mg/dl that does not spontaneously resolve

Technical success:

- successful delivery (i.e., ability to deliver the implant to the intended implantation site, without the need for unanticipated corrective intervention related to delivery);
- successful and accurate deployment, defined as:
 - deployment of the endovascular stent-graft at the intended implantation site;
 - patency of all endovascular graft and stent components; absence of device deformations (e.g., kinks, stent eversion, mal-deployment, misaligned deployment) requiring unplanned placement of an additional device;
 - absence of inadvertent covering of aortic branch vessels; and
- successful withdrawal (i.e., successful withdrawal of the delivery system, without need for unanticipated corrective intervention related to withdrawal)

Thrombus: a blood clot that forms due to injury of a vessel. If the thrombus becomes dislodged and travels it is referred to as an embolus

Treatment success: a composite of technical success and freedom from the following:

- aneurysm enlargement i.e. ≥ 10 -mm as compared to any previous CT measuring orthogonal (i.e., perpendicular to centerline) measurements
- aneurysm-related mortality
- aneurysm rupture

- conversion to open repair
- secondary intervention for migration, type I and III endoleaks, device integrity failure (i.e., fracture), and patency-related events (i.e., device stenosis or occlusion and embolic events)
- Renal failure

Type B – Chronic Dissection: a dissection that takes off distal to the left subclavian artery that is greater than 30 days old

Type B – Subacute Dissection: a dissection that takes off distal to the left subclavian artery that is 15-30 days old

Urgent: An aneurysm requiring repair within 1 week

Visceral arteries (branches): celiac, superior mesenteric, inferior mesenteric, renal arteries

5. Manufacturing Information

The Valiant™ Thoracoabdominal Stent Graft System utilizes the Medtronic TAAA Debranching Stent Graft System. Therefore, the manufacturing information for the system is listed in the following Medtronic regulatory submission:

MAF-2551, Medtronic, TAAA Debranching Stent Graft System Master File

6. Investigator Agreement and Certification

The investigator that will be participating in the study includes [name]. I certify that all participating investigators will sign the investigator agreement and no investigator will be added until the agreement is signed in accordance with 21 CFR 812.29(b)(5).

The names and addresses of investigators will be provided upon request by the FDA and in accordance with 21 CFR 812.150(b) (4).

7. IRB Information

[name], CIP
New York University Institutional Review Board
[name]
[name]

8. Amount to be charged

The amount charged for the devices used in this investigation will be consistent with the amount charged by the manufacturers of the devices to the hospitals.

9. Labeling

The Valiant Thoracoabdominal Stent Graft System utilizes the Medtronic TAAA Debranching Stent Graft System. Therefore, the manufacturing information for the system is listed in the following Medtronic regulatory submission:

MAF-2551, Medtronic, TAAA Debranching Stent Graft System Master File

10. Medicare Generalizability

The Valiant™ Thoracoabdominal Stent Graft System is intended to treat thoracoabdominal aortic aneurysms and the highest incidence of this disease is observed in Medicare eligible patients. A 2013 market survey of inpatient data revealed that 79.8% (1642/2058) of all thoracoabdominal aortic aneurysms occurred in patients over the age of 65. In that same survey, Medicare was the principal payer in 76.3% of those cases and the secondary payer in 82.6% of those cases⁶¹.

Aneurysmal degeneration occurs more commonly in the aging population. Aging may lead to weakening of the aortic wall due to changes in the collagen and elastin. Additionally, comorbidities that may increase the risk for aneurysm formation are smoking, chronic obstructive, pulmonary disease, hypertension, atherosclerosis, male gender, older age, high body mass, genetic disorders, and family history⁶².

11. References

1. Kelly PW. New Stent Grafts for the Thoracic and Thoracoabdominal Segment: The Valiant Thoracoabdominal Design. *J Vasc Surg*. 2016;63(6):228S-229S.

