3.6 Device Description and Drawings

The Visceral Manifold System is made up of two main body components and makes use of several off-the-shelf FDA-approved stent graft components (see Appendix B for system drawing). The two custom main body grafts are the thoracic bifurcation (Figure 1A) and the visceral manifold (Figure 1B). The thoracic bifurcation is deployed in the thoracic aorta and provides the proximal seal for the device. For a Type I or II thoracoabdominal aneurysm the proximal seal is in zone 3, for Type III and V the device seals in zone 4. The two limbs of the thoracic bifurcation allows for continued aortic flow while deploying the visceral segment. The visceral manifold is deployed within the larger 20 mm limb of the thoracic bifurcation to set the stage for the visceral debranching. The branches of the visceral manifold extend to the visceral vessel with the use of covered bridging stents and provide distal seal of the manifold. The smaller 16 mm limb of the thoracic bifurcation extends to the infrarenal segment to either seal in zone 9 for a Type I and V and in zone 10 for Type II, and III. All other connections in the device make use of sizes that are modular and independent of patient anatomy.

Figure 1: Valiant™ Thoracoabdominal Stent Graft System

Aortic components

The thoracic bifurcation stent graft (Medtronic) seals to the native aorta/healthy tissue and bifurcates blood flow in the descending thoracic aorta. The distal end bifurcates into two smaller legs (20 mm and 16 mm) suitable for modular connection to the visceral manifold stent graft and the visceral bypass stent graft. The thoracic bifurcation is composed of a self-expanding, metallic spring scaffold made from nitinol stents sewn to a polyester fabric graft with nonresorbable sutures and is manufactured in the following sizes:

Proximal Diameter (mm)	Target Vessel Diameter Range (mm)	Visceral Perfusion Manifold Diameter (mm)	Visceral Bypass Diameter (mm)	Overall Length (mm)	Catheter Size (Fr)
32	26-29	20	16	118	22
36	30-32			120	25
40	33-36			122	
46	37-42				

Table 1. Thoracic bifurcation dimensions

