4.4.3 Study Endpoints

The primary safety endpoint is freedom from major adverse events (MAE) at 30 days or during hospitalization if this exceeds 30 days.

Major adverse events include death, bowel ischemia, myocardial infarction, paraplegia, renal failure, respiratory failure, and stroke.

The primary effectiveness endpoint is the proportion of the study subjects with treatment success at 1 year. Treatment success is defined as a composite of technical success and freedom from the following:

- Aneurysm enlargement i.e., $\geq 5\text{mm}$ as compared to any previous CT measure using orthogonal (i.e., perpendicular to the centerline) measurements
- Aneurysm rupture
- Aneurysm-related mortality
- Conversion to open repair
- Secondary intervention for migration, Type I and III endoleaks, device integrity failure (e.g., fracture), and patency-related events (i.e., device component stenosis or occlusion and embolic events)

Secondary endpoints include:

- Technical success and the individual components of technical success:
 - Successful delivery
 - Deployment at the intended implantation site
 - Patency of all endovascular graft and stent components
 - Absence of device deformations requiring unplanned placement of an additional device
 - Absence of inadvertent covering of aortic branch vessels
 - Successful withdrawal
- Freedom from the individual components of the primary safety endpoint at 30 days:
 - Death
 - Bowel ischemia
 - Myocardial infarction
 - Paraplegia
 - Renal failure
 - Respiratory failure
 - Stroke
- Freedom from paraparesis at 30 days
- The following at each follow-up interval:
 - Treatment success and the individual components of treatment success including freedom from the following:
 - Aneurysm enlargement
 - Aneurysm-related mortality

- Aneurysm rupture
- Conversion to open repair
- Secondary intervention for migration, type I and III endoleaks, device integrity failure (i.e., fracture), and patency-related events (i.e., device stenosis or occlusion and embolic events).
- Renal failure
- All-cause mortality
- Endoleaks
- Device integrity failure (e.g., fracture)
- Patency-related events (i.e., device stenosis or occlusion and embolic events)
- Other device-related events

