4.4.5.3 Implant Procedures

Note I: For proximal extension of the thoracic bifurcation, two Valiant Captivia or Valiant Navion thoracic grafts can be used. One to extend the landing zone more proximally and one to layer to prevent wear. Deploy the Valiant Captivia or Valiant Navion thoracic grafts according to their respective manufacturer's IFU and continue according to the implant procedures the Medtronic Valiant Thoracoabdominal Stent Graft System IFU.

Note II: For subjects with advanced iliac atherosclerosis and calcification, we will selectively perform use of open conduits to deliver devices, rather than percutaneous approach. We will selectively perform on table Dyna CT – angiograms at the completion of the case. This will give us a better 3-Dimensional image of the stent and help determine if there is any degree of compression, which can be treated at that time with further stenting.

A. The use of thoracic grafts as a method of staging as a pre-operative adjunct procedure.

a. Thoracic Graft Placement

i. This refers to implanting stent-grafts into the thoracic aorta prior to enrollment into the IDE clinical study.

ii. Device Visualization and Preparation

Refer to the Instructions for use provided for the thoracic components to be used.

iii. Device Placement

Ensure that the distal edge of the thoracic graft is 5-7 cm proximal to the celiac artery.

iv. Thoracic Aorta Component Deployment

Follow the study protocol or IFU for deploying the thoracic graft components.

v. Completion

The date of the index procedure will be targeted for within 6 weeks of the thoracic graft placement, but will be based on physician discretion, clinical presentation, and patient compliance.

B. The implantation of the Valiant™ Thoracoabdominal Stent Graft System is conducted under fluoroscopic/angiographic guidance. Refer to the Valiant™ Thoracoabdominal Stent Graft System (IFU) for techniques and methods for device deployment and implantation.

C. The Valiant Thoracoabdominal Stent Graft System may be implanted in a staged procedure per physician discretion (in either a planned or bail-out fashion). The physician may choose to perform the procedure in two or more stages due to the following conditions/scenarios including but not limited to: hypogastric patency, LSA patency, visceral vessel patency, decreased MEP/SEP potentials, at risk dominant segmental arteries, pulmonary status, or any patient whose

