physiologic limitations places them at risk because of the expected length of surgery. The preferred method for planned staging is to create a controlled endoleak which provides limited and temporary perfusion to the aneurysm sac. These methods include but are not limited to placing a bare metal stent in the celiac artery bridge, placing a bare metal stent in the bridge to an alternate visceral artery (ie:SMA or renal), or not completing distal seal in the aorta or iliac arteries.

a. Planned Staged Procedure: Visceral artery bridge endoleak

i. This refers to leaving open a portion of the covered stent bridge between the visceral manifold and target vessel. This is achieved by combining bare metal stents with covered stents to leave ~1-2cm of uncovered conduit along the pathway. This intentional endoleak is resolved in a subsequent intervention where the open portion is covered over by an additional covered stent. It is preferable to achieve this configuration with the bridge to the celiac artery but it can be done in analogous fashion with either the SMA or renal arteries.

ii. Device Visualization and Preparation

Refer to the Instructions for use provided for the bare metal stent for visualization and preparation instruction.

iii. Bridging Stent Deployment

Follow directions in the IFU when deploying bridging stents. Always deploy a covered stent in the leg of the visceral manifold per the VTAAA IFU (9mm iCast at 8atm inflation pressure). When possible, covered stents should be used in the target vessel. The chain of covered stents should be non-continuous in nature with at least one bare metal balloon expandable

stent connecting them. The segment of completely bare stent should be short (~1-2cm) with 2-3cm overlapping with covered stent on either side. Creation of the uncovered segment in as straight a configuration as the anatomy allows will facilitate wire passage during the completion procedure below.

Note: The controlled endoleak should never be created by leaving a visceral manifold limb unconnected to a visceral vessel or with an uncovered segment >2cm due to the pressurization of the aneurysm sac. If a visceral vessel is occluded, the corresponding visceral manifold limb should be plugged with a vascular plug and an alternative (patent) vessel utilized for the staging procedure. The placement of the non-continuous chain of covered bringing stents and a bare metal stent helps direct flow while creating a controlled endoleak.

iv. Completion

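### The 4.9 definitions of conversion to open repair leave out early chest-only repair and late repair without graft removal, so some open repairs can be scored as 1-year treatment success

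*Combined protocol and SAP*

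**What the plan says.** Section 4.4.3 states: "The primary effectiveness endpoint is the proportion of the study subjects with treatment success at 1 year". Treatment success combines technical success with freedom from a list of events, one of which is conversion to open repair. Another is "Secondary intervention for migration, Type I and III endoleaks, device integrity failure (e.g., fracture), and patency-related events".

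Section 4.9 gives conversion two entries and no general one. Early conversion is "any open repair within 30 days of the index procedure involving the vasculature in the abdomen and/or pelvis". Late conversion is "any open surgical repair involving stentgraft removal after 30 days post index procedure". The term also appears in the 4.9 definition of aneurysm-related mortality, where one limb counts deaths within 30 days of, or in hospital after, a conversion.

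Section 3.6 says of the device: "The thoracic bifurcation is deployed in the thoracic aorta and provides the proximal seal for the device". Sections 3.6 and 4.3 place that seal in zone 3 or zone 4, depending on aneurysm type.

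**The concern.** The early definition is limited by body region, and the region it omits is the one that holds the proximal seal. The late definition is limited by whether the graft comes out, which is a surgical choice and not a measure of whether endovascular treatment failed. Followed as written, the two entries let certain open repairs of the treated aorta pass as treatment success. The arms hold 6 and 9 subjects, so one such case visibly changes the reported rate. Section 4.4.7 also plans to pool results with other physician-sponsored studies on the premise of common endpoints, so the definitions need to be ones that every site would apply in the same way.

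**Working it through.** **The plan's own figure.** Treatment success has no target, hypothesis or sample size. The only powered figure is in 4.4.7.1: 46 pooled subjects, at least 80% power, one-sided 2.5%, for a 30-day major adverse event rate of 26% against a goal of 50%. The exact binomial check runs as follows:

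- The largest c with P(X ≤ c | n=46, p=0.50) ≤ 0.025 is c = 15, with exact alpha 0.0129.
- Power = P(X ≤ 15 | n=46, p=0.26) = 88.1%, so the stated figure holds.
- Major adverse events include neither conversion nor secondary intervention, so changing the conversion definitions leaves this figure as it is.

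**Applying the definitions to cases.** In rows 3 and 4, assume that no other component of treatment success occurs.

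| Open repair | Early conversion? | Late conversion? | Caught elsewhere? | Scored |
|---|---|---|---|---|
| 1. Day 10, chest only, for proximal endoleak or migration | No | n/a | Yes, as secondary intervention | Failure |
| 2. Day 10, involving visceral or infrarenal vessels | Yes | n/a | Not needed | Failure |
| 3. Day 10, chest only, for infection or new dissection | No | n/a | No | Success |
| 4. Day 45, graft left in place, for infection or fistula | n/a | No | No | Success |
| 5. Day 45, graft removed | n/a | Yes | Not needed | Failure |

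Rows 3 and 4 are the gap. Dissection and infection are both foreseen as risks in 4.5.1.

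**The 30-day clock.** It runs from the index procedure. Planned stage completion is targeted at 4 to 6 weeks, that is days 28 to 42 (4.4.5.3). An open repair after a planned completion will therefore usually fall under the late definition and count only if the graft is removed.

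**Mortality limb.** If an open repair is not a conversion and not a listed secondary intervention, a death after it is not caught by the conversion limb of aneurysm-related mortality. The other limbs still apply: death within 30 days of, or in hospital after, the index procedure, and death from a complication of the aneurysm or device.

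**Size.** One reclassified subject moves the rate by 100/n points. The table assumes that all other subjects are successes and gives exact (Clopper-Pearson) 95% intervals.

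| n | Shift | As scored now | If counted as failure |
|---|---|---|---|
| 6 | 16.7 | 6/6 = 100% (54.1 to 100) | 5/6 = 83.3% (35.9 to 99.6) |
| 9 | 11.1 | 9/9 = 100% (66.4 to 100) | 8/9 = 88.9% (51.8 to 99.7) |
| 15 | 6.7 | 15/15 = 100% (78.2 to 100) | 14/15 = 93.3% (68.1 to 99.8) |

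If the effectiveness data were pooled to the same 46 subjects (an assumption), the shift would be 100/46 = 2.2 points per subject.

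**The case against.** The strongest reply is that treatment success is a composite and its other parts do most of the work. The secondary-intervention component has no limit by region, surgical route or graft removal, so open chest surgery for migration, a type I or III endoleak, device integrity failure or a patency event already fails. So do rupture, qualifying enlargement and aneurysm-related death. Open bail-out because the device could not be delivered or deployed will usually fail on technical success. Any early repair that also reaches abdominal vessels is a conversion. All of this stands. A reader might infer that device failures in the chest would generally count as success, but the documents do not support that.

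Two further readings are tempting.

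- **Conduits.** Section 4.4.5.3 says "we will selectively perform use of open conduits to deliver devices, rather than percutaneous approach", and the early definition has no access exclusion, so planned iliac conduits might seem to count as conversions. But a conduit is an access step to deliver the graft, and the entry is headed as a conversion. This is an ambiguity, not a definite miscount.
- **Staging.** Of the planned bridge leak, 4.4.5.3 says: "This intentional endoleak is resolved in a subsequent intervention where the open portion is covered over by an additional covered stent". Type IIIb in 4.9 is "leak caused by inadequate seal between modular graft components", and delayed distal seal resembles type Ib, so completions might seem to count as secondary interventions. But the plan does not type these leaks, leaves secondary intervention undefined and calls the second step a completion procedure. The status of completions is unclear; it is not wrongly assigned.

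The endpoint is also reported as a count without a test. With 15 subjects, the conversion column in the annual table and the narrative interim reports (4.7) would probably bring such cases to light. That makes a hidden error less likely, but it does not settle how the case is scored.

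**Conclusion.** The point holds for two kinds of case: early open repair confined to the chest, and late open repair with the graft left in place, each done for a reason that no other component catches. Here the written rule gives the wrong classification, and the error raises the reported success rate. The size is 16.7, 11.1 or 6.7 points per subject for n = 6, 9 or 15. How many such cases will occur cannot be estimated from the documents; the number may be zero.

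There is no consequence for alpha or power. A reader might also calculate that staging caps treatment success at 80%, 60% or 40% if 3, 6 or 9 of 15 subjects are staged. Those caps need both the disputed reading of completions and a staged share that the plan does not give, so they are not a finding. Nor can a net bias be claimed across all readings: missed conversions raise the rate, whereas counting conduits or completions would lower it.

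**What to change.** In 4.9, replace the two entries:

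- *Early conversion:* open repair of the treated aorta or its branches in the chest, abdomen or pelvis within 30 days of the index procedure; access conduits and access-site repair are excluded.
- *Late conversion:* any open repair of the treated segment after 30 days, with or without graft removal.

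As a secondary clarification, state that a planned stage completion is part of the initial treatment and is not a secondary intervention, and state how bail-out completions count.

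These changes concern outcome classification only and should be made before outcomes are classified. The cost is a few sentences. Some open repairs that now pass would count against the device. Because 4.4.7 relies on common endpoints for pooling, the wording should be agreed with the other physician-sponsored studies; failing that, treatment success should be reported under both definitions.
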